### Amendment rationale

This is the first amendment to the protocol. The primary purpose of the current protocol amendment is to extend the duration of the study. The current duration of the original protocol is expected to end as early as May-2022 and no later than Dec-2022. In this amendment the duration of the study is extended to ensure that study patients continue to receive age-appropriate study drug treatment (especially those requiring the pediatric formulations not currently available outside investigational use) and safety follow-up until the expected time when pediatric use of sacubitril/valsartan receives local marketing authorization and becomes commercially available to patients.

First patient first visit of this open-label extension (OLE) study occurred on 02-May-2019. As of 31-Jul-2021, 178 patients have been screened and 173 patients have been enrolled into this study.

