## 1 Introduction

### 1.1 Background

Pediatric heart failure (HF) is characterized by significant morbidity and mortality, frequent hospitalization and medical care, and poor quality of life. It is estimated that between 12,000 to 35,000 children below age 19 are diagnosed with HF in the United States (US) each year ([Hsu and Pearson 2009](#)). Congenital heart disease and cardiomyopathy are the two most common causes of pediatric HF ([Sharma et al 2003](#), [Andrews et al 2008](#)). HF can develop or exacerbate in childhood, during adolescence and later in adulthood as made evident by the growing number of adults with congenital heart disease.

The clinical course and outcome for pediatric HF depends on the etiology. For congenital heart disease, corrective surgery will have a major impact on the clinical course. Following congenital heart surgery, HF can still develop for a number of reasons including myocardial systolic dysfunction.

Many pediatric patients with severe HF are usually listed for heart transplant if available; however, cardiac transplantation is usually a last resort given the limited availability of donor organs, complicated clinical course management and associated morbidity and mortality. In the US, one in four infants listed for heart transplant dies before a donor heart is available ([Mah et al 2009](#)).

In contrast to HF in adults, there is very limited research in pediatric HF. Consequently, the treatment of HF in children is based on information and results provided by adult studies ([Kantor and Mertens 2010](#)). The Diovan Pediatric Heart Failure Survey study confirmed that two factors; 'efficacy shown in an adult trial' and 'Consensus Statements and Guidelines' were the most important factors considered when making treatment decisions for pediatric patients with HF ([CVAL489K2304 HF Survey 2011](#)). According to this survey of pediatric cardiologists, current clinical management of pediatric HF includes angiotensin converting enzyme inhibitors (ACEI), angiotensin receptor blockers (ARBs),  $\beta$ -blockers, diuretics, aldosterone-blocking agents, digoxin and anticoagulants. At present, no trial has demonstrated an outcome benefit of any pharmacotherapy in children with HF.

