**Table 3-2 Study drug dose levels for sacubitril/valsartan**

age groups 1 and 2 *	
Dose levels for pediatric formulation	
Dose level 1	0.8 mg/kg bid.
Dose level 2	1.6 mg/kg bid.
Dose level 3	2.3 mg/kg bid.
Dose level 4	3.1 mg/kg bid.
Dose levels for adult formulation	
Dose level 1	50 mg bid.
Dose level 2	100 mg bid.
Dose level 3	150 mg bid.
Dose level 4	200 mg bid.

\*Note: sacubitril/valsartan target dose (dose level 4) for age groups 1 and 2 is 3.1 mg/kg bid. (see [Section 4.2](#) for additional details).

If a subject is unable to tolerate up-titration to a higher sacubitril/valsartan dose level or at the discretion of the investigator, subjects may be maintained on lower dose levels of sacubitril/valsartan (dose level 1-3, see [Table 3-2](#)). In case of a consecutive 3-month interruption of study treatment, subject should be discontinued from the study and should complete Visit 599.

An outline of the study design is presented in [Figure 3-1](#). Depending on when and where the patient is enrolled, the duration of the study varies from 1 to approximately 4.5 years.

The OLE study drug starting dose will depend either upon the dose of ACEI/ARB that the subject was transitioned to after completion of the PANORAMA-HF or the dose the subject was on at the End of Study visit for the core study PANORAMA-HF prior to screening (Visit 500; refer to [Table 3-2](#)).

At Visit 501, subjects who meet eligibility criteria will start the study drug at dose level 1 or 2 ([Table 3-2](#)). Subjects who were on dose level 1 at the PANORAMA-HF End of Study (PANORAMA-HF visit 416) or who are on a low dose of ACEI/ARB (dose levels 1; [Table 3-3](#)) or not on an ACEI/ARB prior to screening (Visit 500) should start at dose level 1 at Visit 501.

[figure not shown]
Subjects who were on dose level 2, 3 or 4 at PANORAMA-HF visit 416 or who are on a higher dose of ACEI/ARB (dose levels 2, 3 or 4; [Table 3-3](#)) prior to screening (Visit 500) should start at dose level 2 at Visit 501 ([Table 3-2](#)) or at dose level 1 at investigator's discretion.

During the study, visits to assess safety will be conducted at Visit 501 and at 3-months intervals until the conclusion of the study (except for titration visits, which are at 2-week intervals). Unscheduled visits are allowed for subject's safety and for dose adjustment purposes

**Table 3-3 Total daily dose levels of commonly prescribed ACEI/ARBs for the purpose of comparing to dose levels of study drug**

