Total (sum of patient-years) and per-patient duration of exposure to the study treatment will be summarized for each age group and for overall in years, using mean, standard deviation, median, Q1, minimum, Q3 and maximum.

The duration (day) of treatment exposure excluding study drug interruptions is defined as the sum of the duration (day) on dose level 1 to 4 during the study without counting any days that patients are not taking the treatment.

The analyses specified in the Section “Dispensing level (dose level) and daily dose at each visit” will be used here. In addition, the duration of study drug exposure with and without study drug interruptions, respectively, will be categorized into:

- < 6 months
- 6 months to < 1 year
- 1 to < 2 years
- 2 to < 3 years
- 3 to < 4 years
- >=4 years.

The number and percentage of patients within each category by age group and overall will be tabulated.

Duration on each dose level

For a given dose level, the duration (day) on this dose level is defined as the number of days on this dose level during the period from the date of the first dose of the study drug to the date of the last dose of the study drug. In the case that the end date of an earlier dosing interval is the same as the start date of a later dosing interval, the day will be counted as 0.5 day on both the earlier dose level and the later dose level. In the case that the date of permanent discontinuation of the study drug is the same as the date of the last dose of the study drug, the day will be counted as 0.5 day on the dose level of the last dose but not counted on dose level 0.

The median and interquartile range will be presented for duration on each dose level. The number of patients who have ever been on a specific dose level will be reported.

Time to permanent discontinuation of the study drug

The time (day) to permanent discontinuation of the study drug during the study (excluding death) will be summarized for each age group and overall by duration categories (refer to the Section “Duration of study drug exposure” for specific categories) using the Kaplan-Meier curves, considering time-to-death, completion of the study and switch to commercial entresto as independent censoring.

Mean weight based daily dose and mean dose level

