2.14 Interim analysis

No interim analysis is planned. However, the safety will be monitored through regular review of adverse events and related data.

3 Sample size calculation

There is no specific sample size required for the study. All patients who have completed the double-blind phase of the study PANORAMA-HF, as defined in the protocol Inclusion Criteria, and who meet all other Inclusion and Exclusion criteria, are eligible for the extension study.

4 Change to protocol specified analyses

None.

5 Appendix

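### The Kaplan-Meier summary of time to permanent discontinuation censors death, so 1-KM cannot be read as the real-world probability of stopping drug; a cumulative incidence with death as a competing event should be reported

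*SAP*

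**What the plan says.** SAP section 2.4.1, under the paragraph on time to permanent discontinuation, defines the quantity: "The time (day) to permanent discontinuation of the study drug during the study (excluding death) will be summarized". The summary is given for each age group and overall, by exposure-duration categories that run from under 6 months to 4 years and more. The estimator is Kaplan-Meier, and the censoring rule is: "considering time-to-death, completion of the study and switch to commercial entresto as independent censoring".

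No cumulative incidence function or other competing-risk method appears in the SAP, and section 2.5.4 plans no supportive analyses.

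Related outputs are planned elsewhere in the SAP:
- section 2.3.1: the crude number and percentage who discontinue treatment, with primary reasons;
- section 2.8.1: adverse events leading to permanent discontinuation (deaths counted in) and adverse events leading to death;
- section 2.8.2: deaths in the treatment period with primary cause.

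Protocol section 3 states that "the duration of the study varies from 1 to approximately 4.5 years", depending on when and where the patient enrols.

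**The concern.** Death removes a child from the possibility of later stopping the drug, so it is a competing event and not a loss of information about an event still to come. Kaplan-Meier treats a child who died as if he or she remained at the same risk of discontinuing as the children still under observation. The resulting curve describes a population without deaths, and its complement does not estimate the proportion of treated children who stop.

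The protocol's background (section 1.1) gives reason to expect deaths: "Pediatric heart failure (HF) is characterized by significant morbidity and mortality". It also makes independence doubtful. Section 9.1.1 requires treatment to stop where the investigator believes that continuing would harm the child, so a deteriorating child is plausibly at raised risk of both stopping and dying.

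At stake is how the long-term retention figures are read, mainly in the later duration categories, where the gap between the two quantities is widest.

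**Working it through.** The plan states no discontinuation rate, death rate or expected curve, so there is no figure of its own to reproduce. SAP section 3 says: "There is no specific sample size required for the study". The check has two parts: the direction, which needs no rates, and the size, which does.

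**Direction.** Let dH(t) be the estimated discontinuation hazard at time t.
- 1-KM = sum of S_KM(t-) x dH(t), where S_KM falls only at discontinuations.
- Cumulative incidence (Aalen-Johansen) = sum of S_all(t-) x dH(t), where S_all falls at discontinuations and deaths.

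S_all(t-) is never larger than S_KM(t-), so 1-KM is never smaller than the cumulative incidence. It is strictly larger once a discontinuation follows a death.

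An invented example with ten patients shows the mechanism. In time order: death, discontinuation, death, discontinuation, censored, discontinuation, then four censored.
- 1-KM = 1 - (8/9)(6/7)(4/5) = 1 - 0.610 = 39.0%.
- Cumulative incidence = 0.9/9 + 0.7/7 + 0.6/5 = 0.10 + 0.10 + 0.12 = 32.0%.

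**Size.** Inputs: a discontinuation hazard d and a death hazard m, constant over time and independent. Both are assumptions. The time points of 1, 2 and 4 years lie within the follow-up stated in protocol section 3.
- 1-KM = 1 - exp(-d t)
- Cumulative incidence = d/(d+m) x [1 - exp(-(d+m) t)]

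For d = 0.10 and m = 0.10 at 4 years: 1 - exp(-0.4) = 33.0%, against 0.5 x [1 - exp(-0.8)] = 27.5%, a difference of 5.4 points.

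| d / m per year | Excess at 1 year | Excess at 2 years | 4 years: 1-KM vs cumulative incidence | Excess at 4 years | Ratio at 4 years |
|---|---|---|---|---|---|
| 0.05 / 0.02 | 0.05 | 0.2 | 18.1% vs 17.4% | 0.7 | 1.04 |
| 0.08 / 0.05 | 0.2 | 0.7 | 27.4% vs 25.0% | 2.4 | 1.10 |
| 0.10 / 0.10 | 0.5 | 1.6 | 33.0% vs 27.5% | 5.4 | 1.20 |
| 0.15 / 0.08 | 0.5 | 1.9 | 45.1% vs 39.2% | 5.9 | 1.15 |

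Excess is in percentage points. With m = 0 it is zero at every time. Over a wider grid (d from 0.05 to 0.20, m from 0.01 to 0.10) the range is 0.02 to 0.9 points at 1 year, 0.1 to 2.9 at 2 years and 0.4 to 8.5 at 4 years.

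**Simulation check.** The size was set at 173, because the Amendment 1 rationale reports that by 31-Jul-2021 "173 patients have been enrolled into this study"; this is not the final number. Censoring for completion or switch was assumed uniform over 1 to 4.5 years. In five scenarios of 2,000 datasets each, 1-KM at 4 years was never below the Aalen-Johansen estimate. The mean excess for d = 0.10 was 0.6, 1.8, 2.9 and 5.5 points at m = 0.01, 0.03, 0.05 and 0.10, in line with the formulas.

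**The case against.** The strongest reply concerns weight. The primary endpoints are adverse events, laboratory values, vital signs and duration of exposure (protocol section 12.4.1, SAP section 2.5.1). Protocol section 12.3 asks for exposure duration and does not mention time to discontinuation. The curve tests nothing and compares nothing in a single-arm study. This stands. A reader might infer that the main tolerability result of the trial is biased; no section gives the curve that role.

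Second, the crude percentage who discontinue, the deaths, and the adverse events leading to either are all reported separately and are free of this problem. That is true, but the crude percentage takes no account of follow-up that differs between children from 1 to about 4.5 years. It cannot stand in for a time-to-event estimate.

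Third, the SAP states its censoring openly and never says that 1-KM will be presented as the proportion who stopped. The curve may be meant as a no-death summary. That reading is legitimate, but it rests on independence, which is asserted without argument. If the children who die would otherwise have been more likely to stop, the curve is too low for that target. So a reader should not conclude that the estimate is too high under every reading; the upward direction applies to the real-world probability only.

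Fourth, the size is assumed. Entrants had mostly completed 52 weeks on study drug, or had stopped because of the urgent safety measure, and had no significant safety issue in the investigator's judgement. Death hazards of 0.08 to 0.10 per year therefore have no support in the documents. In simulations with 173 children and the same censoring, only about 10 to 19 remain at risk at 4 years and the standard error of 1-KM is roughly 4 to 6 points. The excess is below one standard error in all four tabulated scenarios. This stands as a limit on practical importance. It does not remove the bias, which always has the same sign against the real-world target.

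**Conclusion.** The point holds as a modest correction. With death censored, 1-KM is at or above the real-world cumulative incidence of permanent discontinuation whatever the rates. The alternative no-death reading depends on an independence assumption that the SAP does not defend.

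The size cannot be derived from the documents. In the four tabulated scenarios the excess is about half a point or less at 1 year and at most 1.9 points at 2 years. At 4 years it is 0.7 to 5.9 points, or 4% to 20% in relative terms. These figures assume constant, independent hazards. The excess matters mainly in the categories beyond 3 years, and only if mortality is appreciable.

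The analysis is descriptive and not a primary endpoint. It deserves correction because it is the SAP's only time-to-event summary of retention in a study whose sole objective is long-term safety and tolerability. The criticism is confined to death. Study completion is administrative censoring, and whether censoring at commercial switch is sound is a separate question.

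**What to change.** In SAP section 2.4.1, replace the Kaplan-Meier sentence. Report the Aalen-Johansen cumulative incidence of permanent discontinuation, with death as a competing event and with study completion and switch to commercial product as censoring, by age group and overall, at the existing duration cut-points. If the Kaplan-Meier curve is kept, make it supportive and label it as the hypothetical estimate that would apply if no child died, conditional on independence.

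The cost is one SAP sentence, a standard procedure and one extra output. Dates of death and treatment disposition are already used in the SAP, so no new data are needed. The SAP's change history shows that the censoring rule for this analysis was already revised once, in September 2023. The only downside is that the reported long-term discontinuation figures will be slightly lower than the Kaplan-Meier ones, which the label should explain.

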2.4 Treatments (study treatment, rescue medication, concomitant therapies, compliance)

2.4.1 Study treatment / compliance

All analyses in this section will use the SAF.

The study drug administration is recorded on the CRF page: “Dosage Administration Record” using start date-time, end date-time and dispensing level of the study drug. Each pair of start date and end date will be considered as a dosing interval.

For each patient, the dosing intervals will be sorted according to the start date and the end date of the dose. For subject with gaps and/or overlaps among dosing interval (e.g., when the patient takes the previous dispensing level in the morning and starts a different dispensing level in the evening, the end date of a dosing interval is the same as the start date of the next dosing interval), a conventional data imputation algorithm will be applied to the start date and end date. The detailed algorithm will be provided in the study programming datasets specifications (PDS).

For patients who permanently discontinue study treatment, there should be a dosing interval with its start date equal to the date of the permanent discontinuation of the study drug, its end date equal to the study discontinuation date, and its dispensing level equal to “No treatment”.

Patients who complete the treatment are defined as receiving study treatment as reported in the DAR page until the day of EoS or the date marked as “treatment complete” in the disposition page.

The specific doses based on the dispensing dose levels are defined in [Table 2-1](#) for both the pediatric and adult formulation. If the dispensing level is no treatment, the dose level is defined as 0.

For a dosing interval with a pediatric dose level, the daily dose (mg/day) during the interval is defined as the product of the weight based daily dose (mg /kg/day) during the interval and the weight during the interval, where the weight based daily dose (mg /kg/day) during the interval is defined in [Table 2-1](#) and [Table 2-2](#) and the weight during the interval is defined as the weight from the last non-missing assessment (scheduled or unscheduled) prior to or equal to the start dose time of the study drug of the interval.

Table 2-1 Study drug dose levels and doses for sacubitril/valsartan

Age groups 1 and 2 *		
Dispensing dose levels for pediatric formulation		Weight based daily dose
Dose level 1	0.8 mg/kg bid.	1.6 mg/kg/day
Dose level 2	1.6 mg/kg bid.	3.2 mg/kg/day

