For each patient, the mean weight based daily dose (mg/kg/day) during the study is defined as the weighted mean of the weight based daily dose (mg/kg/day) among dose level 0 to 4 using the duration (day) on each dose level as the weight, i.e.

$$\frac{\sum_{k=0}^4 \text{Weight Based Daily Dose (mg/kg/day)} \text{ for Dose Level } k \times \text{Duration (day) on Dose Level } k}{\sum_{k=0}^4 \text{Duration (day) on Dose Level } k}$$

the mean dose level is defined as the weighted mean of the dose level among dose level 0 to 4 using the duration (day) on each dose level as the weight, i.e.,

$$\frac{\sum_{k=0}^4 k \times \text{Duration (day) on Dose Level } k}{\sum_{k=0}^4 \text{Duration (day) on Dose Level } k}$$

The mean weight based daily dose (mg /kg/day) and the mean dose level during the study will be summarized for each age group and overall, using number of observations, mean, standard deviation, median, minimum, Q1, Q3, and maximum.

Dose down titration

A down-titration dosing interval is defined as a dosing interval whose dose level is changed to a lower dose level from its previous dosing interval.

The dose down titration during the study will be summarized by each age group and overall, using the numbers and percentages of patients with at least one down-titration dosing interval during the study.

Dose interruption

A dose-interruption dosing interval is defined as a dosing interval with “NO TREATMENT”.

The numbers and percentages of patients with at least one dose-interruption greater than 24-hour dosing interval during the study will be provided by age group and the overall.

The numbers and percentages of patients having at least one dose-interruption dosing interval with duration (day) of dose-interruption larger than 14 days will be provided by each age group and overall.

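### The SAP's down-titration count takes in interruptions and permanent stops, and its interruption count takes in permanent stops, because no treatment is coded as dose level 0

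*SAP*

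**What the plan says.** All the relevant rules are in SAP 2.4.1 (Study treatment / compliance).

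- **Coding of no treatment:** "If the dispensing level is no treatment, the dose level is defined as 0".
- **Permanent discontinuation:** "there should be a dosing interval with its start date equal to the date of the permanent discontinuation of the study drug". That interval runs to the study discontinuation date and carries the no-treatment dispensing level, so it is level 0.
- **Down-titration:** "a dosing interval whose dose level is changed to a lower dose level from its previous dosing interval". The table reports patients with at least one such interval during the study.
- **Interruption:** "A dose-interruption dosing interval is defined as a dosing interval with" the no-treatment dispensing level. The table reports patients with at least one interruption longer than 24 hours, and patients with at least one longer than 14 days.

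The same section treats 0 as a genuine dose level when it averages the dose level over levels 0 to 4. Where it wants 0 left out, as in exposure excluding interruptions, it names levels 1 to 4. It confines duration on each dose level to the span from first to last dose. The down-titration and interruption counts carry neither limit.

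**The concern.** Level 0 is below levels 1 to 4. Read literally, a patient who stops the drug for a few days and resumes the same dose counts as down-titrated, and so does a patient who stops for good from the target dose. The protocol (6.5.1, on adjusting the dose level and on restarting) handles lowering the dose, stopping temporarily and stopping permanently as different steps. SAP 2.8.1 likewise names dose adjustment, temporary interruption and permanent discontinuation separately.

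What is at stake is whether two tolerability tables can be read as labelled. Patients here are titrated according to tolerability, and the only objective is safety and tolerability. A reader will take the down-titration percentage as the share of patients whose dose had to be lowered, and the interruption percentage as the share with a temporary stop. As defined, neither is that.

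**Working it through.** The plan gives no figure for either percentage, so there is nothing to reproduce. The check applies the rules to example histories and then bounds the effect under assumed rates.

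**Step 1: rules applied to hypothetical dose sequences.** As written, interval *i* is a down-titration if level(*i*) < level(*i*−1), with no treatment = 0. The corrected rule ignores level-0 intervals and compares each non-zero level with the last non-zero level. The interruption column ignores the 24-hour and 14-day thresholds.

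| Sequence | Meaning | Down-titration as written | Down-titration corrected | Meets interruption definition as written |
|---|---|---|---|---|
| 2-3-4-3 | dose reduced | yes | yes | no |
| 2-3-4-0-4 | interrupted, same dose resumed | yes (at the 0) | no | yes |
| 2-3-4-0-2 | interrupted, restarted lower | yes (at the 0, not at the 2) | yes (at the 2) | yes |
| 2-3-4-0 | permanently stopped | yes (at the 0) | no | yes |
| 2-3-4-0-0 | interrupted, then permanently stopped | yes (at the first 0) | no | yes |
| 2-3-4-0-2-3-4 | interrupted, restarted lower, re-titrated | yes (at the 0) | yes (at the 2) | yes |
| 2-3-4 | never reduced | no | no | no |

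The written rule flags 6 of 7 patients and the corrected rule 3 of 7. The three that drop out never took a reduced dose. Every patient flagged by the corrected rule is also flagged by the written one, so the error runs in one direction.

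**Step 2: the interruption count.** The fourth sequence has no temporary interruption, yet its final interval qualifies as one. It passes a threshold if study discontinuation date − date of permanent discontinuation exceeds 24 hours or 14 days. The documents do not say how often that happens.

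**Step 3: size under assumed rates.** Let *d*, *i* and *p* be the proportions of patients with a true reduction, an interruption and a permanent discontinuation. The down-titration percentage as written is the proportion with any of the three:

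- full overlap: max(*d*, *i*, *p*)
- no overlap: *d* + *i* + *p*
- independence: 1 − (1 − *d*)(1 − *i*)(1 − *p*)

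| Assumed *d* / *i* / *p* | Full overlap | Independence | No overlap |
|---|---|---|---|
| 10% / 5% / 5% | 10% | 1 − 0.90 × 0.95 × 0.95 = 19% | 20% |
| 10% / 10% / 15% | 15% | 1 − 0.90 × 0.90 × 0.85 = 31% | 35% |
| 10% / 15% / 20% | 20% | 1 − 0.90 × 0.85 × 0.80 = 39% | 45% |

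The true reduction rate is 10% in every row. In the first row, full overlap gives no inflation at all: the excess depends on how many patients stop without ever having a reduced dose.

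**The case against.** **These are minor outputs.** The named primary endpoints are adverse events, laboratory values, vital signs and duration of exposure, and protocol 12.4 bases the primary safety assessment on adverse events. Protocol 12.3 does not list down-titration or interruption percentages. Tolerability is also described by adverse events leading to dose changes or stopping, dose level by visit, time on each level and time to permanent discontinuation. This stands. A reader might infer that the study's main tolerability result is compromised; the documents do not support that.

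**A reduced-dose restart is not lost.** In the sequence 4, 0, 2 the restart is scored as a rise, and a reader might infer that the rule also misses true reductions. It does not. The table counts patients with at least one qualifying interval, and this patient was already flagged at the 0. The restart matters only for how the repair is worded.

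**Independence is doubtful.** Protocol 6.5.1 describes temporary discontinuation as a step after down-titration has failed, so the same patients may well have both. This stands, and it is why a range is shown. A reader might infer from the 31% figure that the rate is tripled; that ratio comes from the chosen inputs.

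**The final no-treatment interval may be short.** The protocol asks for Visit 599 as soon as possible after premature discontinuation, so it may seldom exceed 14 days. That is fair; the frequency is unknown.

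**The intent may be clear, or set out elsewhere.** One bullet in protocol 6.5.1 runs down-titration and discontinuation together, so the separation there is not perfectly clean. The programming datasets specifications, not available here, might exclude level 0. But for dosing intervals the SAP defers only the date algorithm for gaps and overlaps to them, and its definition of down-titration is complete as it stands.

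**Conclusion.** The point holds on the SAP's own wording. Any interruption or permanent discontinuation that is recorded as a no-treatment interval after an active dose counts as a down-titration. The reported percentage can overstate dose reduction and cannot understate it. The interval created at permanent discontinuation also counts as an interruption if it lasts long enough.

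The size cannot be determined from the documents. On the assumed 10% / 10% / 15% rates it is 15% to 35% reported against 10% true. The conclusion assumes that the SAP is programmed as written and that stops are entered as no-treatment intervals. It concerns the labelling of two descriptive tables; no hypothesis test, primary endpoint or sample size depends on it. It should be corrected because the percentages would otherwise be misread and the repair is easy.

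**What to change.** In SAP 2.4.1:

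1. **Down-titration:** define it as a dosing interval at a non-zero dose level lower than the most recent preceding non-zero level. Both parts are needed. Excluding level 0 alone, while still comparing with the immediately preceding interval, would lose the true reduction in 4, 0, 2.
2. **Interruption:** exclude only the no-treatment interval that starts on the date of permanent discontinuation. Keep any interval that began as a temporary interruption, even if the drug was never restarted, for example withdrawal after a consecutive 3-month interruption or death while off drug. Requiring a later non-zero interval would wrongly delete these.
3. **Interruptions that become permanent:** state which date is taken as the date of permanent discontinuation, so that rule 2 can be programmed without judgement.

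The cost is a few sentences of SAP text and a small programming change. The Dosage Administration Record already collects the levels and dates, so no new data are needed.
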